14.3. Subject Information and Informed Consent

Written informed consent must be obtained from each subject in accordance with the ICH GCP. Informed consent must be obtained prior to performing any study-specific procedures. The consent form that is used must be approved by both the reviewing IRB/ethics committee and Pulmotect.

The subject and the individual explaining the study will sign the current IRB/ethics committee-approved version of the consent form. A copy of the signed consent form will be given to the subject. The date that consent was obtained will be recorded on the eCRF as well as in the subject's source documents.

A copy of each version of the informed consent form that has been approved by the IRB/ethics committee will be provided to the Sponsor. Care should be taken that the current approved version of the consent form is provided to the subject for review and signature. It is possible that in some cases an updated consent form will contain significant information that will require a previously enrolled subject to sign the updated consent form. Original signed consent forms must be in the Site Regulatory File and be available for review by authorized individuals.

A sample consent form is provided in Section 15.

14.4. Data Safety Monitoring Board

An external DSMB will be used to evaluate safety of the study in an ongoing manner. There will be three voting members. None of the voting members will have any affiliation with Pulmotect, Inc. A full description of the membership, role, and responsibilities of the DSMB will be finalized prior to the start of the study, and will be provided in the DSMB charter. The DSMB will evaluate safety at regular intervals including early in the trial.

The DSMB chair has the ability to pause study enrollment at any point during the study for any reason including rapid enrollment which could hinder the DSMB's ability to review the safety of PUL-042 Inhalation Solution in a timely manner relative to overall enrollment. The first evaluation will be done after 40 subjects have completed dosing. Unless the DSMB recommends to the contrary, enrollment will be allowed to continue until 80 patients have completed dosing. Enrollment beyond 80 subjects will require formal DSMB review of the data from the first 40 subjects to have been completed with explicit approval to continue enrollment beyond 80 subjects. Subsequent evaluations will occur at 120 patients with further ad hoc meetings at the discretion of the DSMB.

One potential recommendation of the DSMB is to stop the study due to safety concerns. Any imbalance in the incidence of AEs between placebo and active treatment is to be further reviewed by the DSMB taking into account the totality of evidence in order to render a recommendation to the sponsor regarding study continuation. As specified in the DSMB charter the formal review of data will take place at each meeting of the DSMB after 40, 80 and 120 subjects have completed dosing. Ad hoc meetings can also be called.

As a further effort to ensure the safety of PUL-042, a stopping rule that is based only on mortality will be employed. This rule will be implemented if there is a high probability of excess mortality risk among patients randomized to PUL-042. The following hierarchical analysis of mortality will be performed after 50% of subjects have been enrolled (50/group) and followed up for 28 days from the start of investigational therapy:

1) Based on blinded data, if no more than 3 deaths have occurred during the study this analysis will not be conducted due to the lack of evidence of increased mortality risk attributable to PUL-042.

If more than 3 deaths occur:

- 2) The Unblinded statistician will evaluate unblinded mortality data to determine the treatment specific death rate (i.e., $D_{Tx} = Deaths_{Tx} / N_{Tx}$; Tx = Active or Placebo).
- 3) If the difference, Δ , in treatment-specific death rates (i.e., $\Delta = D_{Active} D_{Placebo}$) is greater than 7.5%, the DSMB will further review the totality of evidence and render a recommendation to the sponsor regarding study continuation.

Characteristics of this rule are as follows:

Assuming that the true underlying control arm mortality rate is 5% and using a normal approximation when comparing proportions, the probability of stopping is approximately:

- 90% if the true underlying mortality rate attributable to PUL-042 is 25%.
- 62% if the true underlying mortality rate attributable to PUL-042 is 15%.
- only 11% if the true underlying mortality rate attributable to PUL-042 is 5% (equal to the assumed true underlying control arm mortality rate)

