13. STATISTICAL METHODS

13.1. Sample Size Determination

The trial size of 200 subjects (100 PUL-042 inhalation solution: 100 placebo) was chosen based on clinical considerations. The rates of infection to adequately estimate a sample size for a statistically significant result are unknown.

Enrolled subjects will be randomized with equal probability to receive blinded treatment consisting of either PUL-042 or placebo.

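### The mortality rule's characteristics are given only at an unsupported 5% control death rate; if mortality is much lower, the rule has little sensitivity to a several-fold excess.

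*Protocol*

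**What the plan says.** Protocol 14.4 adds a mortality-only rule to the DSMB's safety reviews, and SAP 8 repeats it. It is applied once, "after 50% of subjects have been enrolled (50/group) and followed up for 28 days". It has two steps.

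- **Blinded gate:** "if no more than 3 deaths have occurred during the study this analysis will not be conducted due to the lack of evidence". The evidence said to be lacking is that PUL-042 raises the risk of death.
- **Threshold:** with more than 3 deaths, an unblinded statistician computes the death rate by arm. If active minus placebo "is greater than 7.5%, the DSMB will further review the totality of evidence" and makes a recommendation to the sponsor.

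The operating characteristics rest on one scenario: "Assuming that the true underlying control arm mortality rate is 5% and using a normal approximation when comparing proportions". The printed probabilities of stopping are about 90%, 62% and 11% for active mortality of 25%, 15% and 5%.

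Other sections bear on this:

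- **Protocol 7.2.1 and 7.2.2:** entrants score 0 on the Ordinal Scale and on each symptom, have FEV1 and FVC of at least 70% predicted, and have no chronic lung disease, pulmonary hypertension or heart failure.
- **Protocol 13.1:** "The rates of infection to adequately estimate a sample size for a statistically significant result are unknown".
- **Protocol 11.1:** the DSMB reviews unblinded data at 40, 80 and 120 subjects, and ad hoc on request.
- **Protocol 12 and 12.4:** symptoms and events of SARS-CoV-2 infection are captured on the symptom score and the Ordinal Scale, and are not to be reported as adverse events.

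**The concern.** The printed probabilities tell a reader, an ethics committee or the DSMB how well the rule would detect excess deaths. They hold only if about 1 placebo subject in 20 dies within 28 days. Neither document gives a source for that rate, an expected death rate, or any result at a lower one.

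If deaths are rare, a fixed 7.5-point difference is a high bar at 50 per group, and the rule would give much less protection than its stated characteristics suggest. The gate has a separate effect. With three deaths on active and none on placebo, the rule makes no comparison by arm, and the text calls this an absence of evidence.

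This matters more because the other trigger named in Protocol 14.4 is an imbalance in adverse events. COVID-19 events are kept out of adverse event reporting, so worsened COVID-19 might not show up there.

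**Working it through.** **Inputs.** n = 50 per group, threshold 0.075, gate of more than 3 deaths in total, and control mortality 5%, all from Protocol 14.4 and SAP 8. Control rates below 5% and infection rates are my assumptions.

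**1. The plan's own figures.** The normal approximation for a fixed-difference rule is P = Φ((pA − pP − 0.075)/SE), with SE = √(pA(1−pA)/n + pP(1−pP)/n) and pP = 0.05.

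| Active rate | SE, n = 50 | z | P, n = 50 | Exact binomial with gate, n = 50 | P, n = 25 | Printed |
|---|---|---|---|---|---|---|
| 25% | 0.0686 | 1.823 | 96.6% | 97.3% | 90.1% | 90% |
| 15% | 0.0592 | 0.423 | 66.4% | 69.1% | 61.8% | 62% |
| 5% | 0.0436 | −1.721 | 4.3% | 5.2% | 11.2% | 11% |

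The printed set is not reproduced at the stated 50 per group. Pooled variance and continuity corrections at 50 per group do not reproduce it either. The same formula at 25 per group matches all three figures.

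**2. What 5% implies.** If all deaths come through infection, fatality among the infected = 5% ÷ infection rate. That is 5% if everyone is infected, 17% if 30% are, 25% if 20% are, and 50% if 10% are.

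**3. What the threshold needs.** 0.075 × 50 = 3.75, so active must exceed placebo by at least 4 deaths. Total deaths are then at least 4, and the gate is always passed whenever the threshold is crossed. The exact trigger probabilities are identical with and without the gate.

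**4. Sensitivity at other control rates.** This is the exact double-binomial sum of P(total deaths > 3 and difference > 0.075), with n = 50 per group.

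| Control rate (assumed below 5%) | No excess | Three-fold | Five-fold |
|---|---|---|---|
| 0.1% | <0.001% | 0.002% | 0.01% |
| 0.25% | 0.001% | 0.05% | 0.3% |
| 0.5% | 0.01% | 0.5% | 3.0% |
| 1% | 0.1% | 4.3% | 18.0% |
| 2% | 0.8% | 21.1% | 57.2% |
| 5% | 5.2% | 69.1% | 97.3% |

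A 50% chance of triggering needs active mortality of 7.8% at control 0.5%, 8.2% at control 1%, and 9.2% at control 2%.

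**5. The 3-0 split.** At a 0.5% death rate, the probability of three or more deaths among 50 is 1 − P(0) − P(1) − P(2) = 0.2%. That is an unusual result at that rate, yet if there are no placebo deaths, three active deaths stop at the gate.

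**The case against.** The strongest reply is that the rule is an addition to DSMB oversight. A reader might infer that a 3-0 split would go unseen. The documents do not support that: Protocol 11.1 gives the DSMB unblinded data at three scheduled points, and ad hoc meetings are allowed. The gate cancels only the rule's own comparison. What remains is that neither document says deaths or Ordinal Scale scores are tabulated by arm at those reviews. The DSMB charter, which might say so, is not among the documents.

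A reader might also blame the gate for the insensitivity. Step 3 of the working shows that it plays no part in it.

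It is tempting to say that the rule almost never fires in healthy contacts. Both halves go too far. The entry criteria do not require good general health: there is no upper age limit, cohabitants must be 50 or older, and Protocol 13.3 lists comorbidities as a possible covariate. The trigger chance also reaches 18% for a five-fold excess at control 1%, and 57% at control 2%.

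Part of the weakness is sample size. At 0.5% versus 1.5%, the expected deaths are 0.25 and 0.75, and even a trigger at three active deaths would fire only about 4% of the time.

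Fast enrolment could in principle outrun the single look, but the DSMB may pause enrolment, and going beyond 80 subjects needs its explicit approval. I do not rely on that scenario.

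**Conclusion.** The point holds in this form. The rule's characteristics are stated at one control death rate that has no support in the documents. Because of the 7.5-point threshold at 50 per group, sensitivity falls steeply as that rate falls: for a three-fold excess, from 69% at control 5% to 21% at 2%, 4% at 1% and 0.5% at 0.5%. The documents give no death rate, so they cannot show which row applies. That is why a range is needed.

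The printed figures are also wrong for the stated group size at 5% itself, where the rule performs better than printed (97/69/5% exact against 90/62/11%).

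The consequence is moderate. Crossing the threshold prompts a review and does not stop the study, and the DSMB has other unblinded reviews. The remaining gap is that the adverse event review may miss worsened COVID-19, and that the gate's wording describes a small, one-sided death count as no evidence.

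**What to change.** Make the same changes in Protocol 14.4 and SAP 8, and carry them into the DSMB charter.

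1. Restate the characteristics at 50 per group for control mortality from 0.1% to 5%, labelled as an assumed range. Recompute the 5% row: 96.6/66.4/4.3% by the stated normal approximation, or 97/69/5% exact.
2. State that deaths and Ordinal Scale scores of 3 or more are tabulated by arm for the DSMB at each scheduled unblinded review, whatever the pooled death count. Remove the phrase that equates three or fewer deaths with absent evidence.
3. Ask the DSMB to consider whether a review trigger on Ordinal Scale 3 or more should supplement the mortality rule. The scale is already collected at every visit and includes death. Any gain would come from such events being more common than deaths, because at equal event rates the trigger probabilities are the same as in the table above. Whether to add it, and at what threshold, is for the DSMB.

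The cost is wording and one table, with no new data collection. The stated detection figures at low death rates will look less favourable, and a few more DSMB reviews may follow.

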8. INTERIM ANALYSES

An external DSMB will be used to evaluate safety of the study in an ongoing manner. A full description of the membership, role, and responsibilities of the DSMB is provided in the DSMB charter. As specified there, a formal review of data will take place at DSMB meetings scheduled to occur after 40, 80 and 120 subjects have completed dosing.

As a further effort to ensure the safety of PUL-042, a stopping rule that is based only on mortality will be employed. A recommendation to stop the study would be made only if there is a high probability of excess mortality risk among subjects randomized to PUL-042. The following hierarchical analysis of mortality will be performed after 50% of subjects have been enrolled (50/group) and followed up for 28 days from the start of investigational therapy:

1) Based on blinded data, if no more than 3 deaths have occurred during the study this analysis will not be conducted due to the lack of evidence of increased mortality risk attributable to PUL-042.

If more than 3 deaths occur:

- 2) The Unblinded statistician will evaluate unblinded mortality data to determine the treatment specific death rate (i.e., $D_{Tx} = \text{Deaths}_{Tx} / N_{Tx}$; Tx = Active or Placebo).
- 3) If the difference, Δ , in treatment-specific death rates (i.e., $\Delta = D_{Active} D_{Placebo}$) is greater than 7.5%, the DSMB will further review the totality of evidence and render a recommendation to the sponsor regarding study continuation.

Characteristics of this rule are as follows:

Assuming that the true underlying control arm mortality rate is 5% and using a normal approximation when comparing proportions, the probability of stopping is approximately:

- 90% if the true underlying mortality rate attributable to PUL-042 is 25%.
- 62% if the true underlying mortality rate attributable to PUL-042 is 15%.
- only 11% if the true underlying mortality rate attributable to PUL-042 is 5% (equal to the assumed true underlying control arm mortality rate).

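### The stated trigger probabilities of the mortality rule (90%, 62%, 11%) match 25 per group; at the planned 50 per group they are about 97%, 66% and 4%.

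*Protocol*

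**What the plan says.** Protocol 14.4 and SAP 8 describe the same mortality rule. It is to be "performed after 50% of subjects have been enrolled (50/group) and followed up for 28 days from the start of investigational therapy". It is gated on blinded data: "if no more than 3 deaths have occurred during the study this analysis will not be conducted". If there are more than 3 deaths, an unblinded statistician computes the death rate in each arm. If active minus placebo exceeds 7.5%, "the DSMB will further review the totality of evidence and render a recommendation to the sponsor regarding study continuation".

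Both documents then describe how the rule behaves. They assume 5% control mortality and say that, "using a normal approximation when comparing proportions, the probability of stopping is approximately":

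- "90% if the true underlying mortality rate attributable to PUL-042 is 25" percent
- "62% if the true underlying mortality rate attributable to PUL-042 is 15" percent
- "only 11% if the true underlying mortality rate attributable to PUL-042 is 5" percent

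The last case is the one with equal mortality in the two arms.

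**The concern.** Method, threshold, control rate and group size are all given, so the three probabilities can be checked without any added assumption. They looked too low at the top and too high at the bottom for 50 per group, which is the pattern produced by a smaller sample.

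This is the only quantitative trial-level stopping rule in the two documents, and these three lines are the only account of how it performs. A DSMB member, ethics committee or regulator would take from them that the rule misses a rise to 25% mortality in one trial in ten, and that it triggers in about one trial in nine when the drug does nothing to mortality. If those figures belong to a different look size, either they are wrong or the stated timing is.

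A smaller point is the label. The figures are called a probability of stopping, but crossing 7.5% leads only to a review and a recommendation.

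**Working it through.** **Inputs**

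- Group size n = 50 (Protocol 14.4, SAP 8). This is half of the planned 100 per arm: "The trial size of 200 subjects (100 PUL-042 inhalation solution: 100 placebo) was chosen based on clinical considerations" (Protocol 13.1).
- Threshold: difference above 0.075, active minus placebo (Protocol 14.4, step 3).
- Control mortality 0.05; PUL-042 mortality pA = 0.25, 0.15 or 0.05.
- Gate: more than 3 deaths in total.

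**Formula (normal approximation, unpooled variance)**

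SE = √{[pA(1 − pA) + 0.05 × 0.95] / n}

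P(trigger) = 1 − Φ{[0.075 − (pA − 0.05)] / SE}

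**Reproducing the stated figures.** They come out at n = 25:

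- pA = 0.25: SE = √(0.235/25) = 0.0970; z = −0.125/0.0970 = −1.289; P = 90.1%
- pA = 0.15: SE = √(0.175/25) = 0.0837; z = −0.025/0.0837 = −0.299; P = 61.7%
- pA = 0.05: SE = √(0.095/25) = 0.0616; z = 0.075/0.0616 = 1.217; P = 11.2%

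**At the documents' own n = 50:**

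- pA = 0.25: SE = √(0.235/50) = 0.0686; z = −1.823; P = 96.6%
- pA = 0.15: SE = √(0.175/50) = 0.0592; z = −0.423; P = 66.4%
- pA = 0.05: SE = √(0.095/50) = 0.0436; z = 1.721; P = 4.3%

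**Solving each stated figure for n**, with n = [z / (pA − 0.05 − 0.075)]² × [pA(1 − pA) + 0.0475]:

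- 90%: (1.2816/0.125)² × 0.235 = 24.7
- 62%: (0.3055/0.025)² × 0.175 = 26.1
- 11%: (1.2265/0.075)² × 0.095 = 25.4

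If each stated figure may be off by half a point from rounding, the ranges are 23.6–25.8, 23.9–28.4 and 24.3–26.5. With equal groups, 25 is the only whole number in all three.

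**Other readings**

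| Calculation | pA = 25% | pA = 15% | pA = 5% |
|---|---|---|---|
| Stated in both documents | 90% | 62% | 11% |
| n = 50, unpooled | 96.6% | 66.4% | 4.3% |
| n = 50, pooled variance | 96.0% | 66.2% | 4.3% |
| n = 50, continuity correction 1/(2n) | 95.3% | 60.0% | 2.6% |
| n = 50, continuity correction 1/n | 93.7% | 53.4% | 1.5% |
| n = 50, PUL-042 rate read as added to the 5% | 99.3% | 87.8% | 31.7% |
| n = 50, exact binomial with the gate | 97.3% | 69.1% | 5.2% |
| n = 25, unpooled | 90.1% | 61.7% | 11.2% |
| n = 25, exact binomial with the gate | 90.5% | 57.5% | 6.4% |
| n = 25, exact binomial without the gate | 93.0% | 68.0% | 15.4% |

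No single different threshold works at n = 50 either. The figures 90%, 62% and 11% would need thresholds of 11.2%, 8.2% and 5.4% respectively.

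The scheduled DSMB reviews, at 40, 80 and 120 subjects, are about 20, 40 and 60 per group. The same formula gives about 88/61/14%, 95/65/6% and 98/68/3%, so none of these looks is the source.

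**Role of the gate.** At 50 per group, 3/50 = 6% is below the threshold and 4/50 = 8% is above it. A trigger therefore needs at least 4 more deaths on active, which already passes the gate, so the gate never blocks one. At 25 per group an excess of 2 deaths (2/25 = 8%) would be enough, and the gate would block many triggers; with equal 5% mortality it cuts the exact rate from 15.4% to 6.4%. The gate as written therefore sits more naturally with 50 per group.

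**The case against.** The best case on the other side accepts the arithmetic and disputes how much it matters.

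- **The error is conservative.** As written, the rule is more sensitive and triggers falsely less often than stated, and no efficacy analysis uses the figures. This stands.
- **Participant protection does not rest on these lines.** The DSMB reviews unblinded data at 40, 80 and 120 subjects, can meet ad hoc and can pause enrollment. The 7.5% trigger is an additional safeguard. This also stands.
- **The figures are given as approximate, and 62% against 66% is a modest gap.** That is fair for the middle figure. It does not cover 11% against 4.3%, or 90% against 96.6%.
- **At 5% mortality the normal approximation is rough,** with 50 × 0.05 = 2.5 expected deaths per arm. Against the exact 5.2% the overstatement is about 2.1-fold rather than 2.6-fold. This is a good reason to report the exact values as well; it does not rescue 11%.
- **The origin at 25 per group is inferred.** True: neither document states it, and near-equal splits around 25 would also fit. The defect does not depend on the inference, since the figures fail at 50 per group whatever their source.
- **The label is unlikely to mislead,** because step 3 sits directly above the figures. Relabelling is secondary to correcting the numbers.

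**Conclusion.** The concern holds. With the documents' own inputs, the three probabilities are about 97%, 66% and 4%, not 90%, 62% and 11%. Put as error rates, the rule would fail to trigger in about 3% of trials rather than 10% when PUL-042 mortality is 25%. It would trigger in about 4–5% rather than 11% when both arms have 5% mortality. The largest relative discrepancy is that last one: 11/4.3 = 2.6-fold by the stated method.

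This rests on a look at 50 per group with equal arms, a strict 7.5-point threshold and 5% control mortality, all of which both documents state. It is a worthwhile correction to descriptive text in two governing documents. It is not evidence that the rule is unsafe, and crossing the threshold remains non-binding.

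**What to change.** The sponsor should first confirm that the analysis is meant to take place at 50 per group.

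- **If so,** replace the three figures in Protocol 14.4 and SAP 8 with about 97%, 66% and 4% by the stated normal approximation. Preferably give the exact binomial values beside them (97%, 69%, 5%). Describe them as the probability of triggering DSMB review of the totality of evidence.
- **If another look size was intended,** reconcile the timing text with the figures in both documents. If that look size is 25 per group, recompute with the gate included, since it then changes the probabilities.
- **In either case,** check whether the DSMB charter, which is not among these documents, repeats the same figures.

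If 50 per group is confirmed, the cost is three numbers and one label in two documents, plus the charter check. The gate, the 7.5% threshold, the timing and the conduct of the trial stay as they are.

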14.5. Adherence to the Protocol

The study shall be conducted as described in this protocol except for an emergency situation in which proper care of the subject requires immediate alternative intervention. This protocol refers to the protocol as provided by Pulmotect and approved by both the IRB/ethics committee and submitted to the FDA as part of the Investigational New Drug Application that is in effect. While FDA regulations permit the protocol to be amended, this must be done in accordance with the provisions agreed upon in Section 14.6.

Any material deviation from study procedures (identified by site personnel or monitor) will be documented. Major subject-level deviations will be captured on the protocol deviation form in the eCRF. A list of protocol deviations will be compiled and reviewed by the Principal Investigator and Sponsor to identify major and minor deviations periodically using the following criteria:

Major – A serious breach of protocol and GCP compliance, which may also impact subject safety or study endpoints. Examples include (but are not limited to):

- Violation of inclusion/exclusion criteria
- Dose calculation error
- Failure to collect primary endpoint data

Minor – An administrative breach of protocol procedure that has minimal impact on regulatory compliance, subject safety, or study endpoints. Examples include (but are not limited to):

- Visits conducted out of established timeframes
- Dose timing out of established timeframes
- Missing selected laboratory panel parameters

